6. SAFETY MONITORING AND ASSESSMENT

Risks of intervention study

Spirometry is a breathing test commonly utilized in the outpatient primary care setting. Risks and discomforts associated with spirometry are possible. The risks include shortness of breath and on rare occasion, the subject might experience dizziness, cough, or light-headedness. A medication that can open subjects' airways may be used during spirometry testing. This medication, albuterol, is in a class of medications (i.e. short acting beta agonist) that is often used to treat subjects suspected with COPD and/or asthma as part of usual care. Albuterol may sometimes cause tremors/shaking, nervousness, dizziness, difficulty sleeping, headache, irregular heartbeats, drying or irritation of mouth, sore throat, upset stomach, and coughing. These effects usually disappear within a short time and do not require treatment.

Data Safety Monitoring Plan

The PI will review monthly data reports reviewing recruitment, consent, intervention activities, adverse events, and follow-up. Although few, if any, intervention-related adverse events are anticipated in this study, the study population is at risk for poor outcomes, including life-threatening exacerbations and death not caused by the study itself. The PI will comply with prompt reporting of any adverse event to the IRB

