2. If the spirometry findings are normal, with approval from the PCP, will de-escalate respiratory medication therapy via a stepwise process and schedule patient back for a repeat pre and post bronchodilator spirometry within 1-2 weeks at the same time and place as the PCP clinic session or the CRC (Clinical Research Center at UIC). Again with the PCP approval, this

deescalation and repeat spirometry can occur in 1-2 week intervals until all maintenance medications are discontinued as long as the pre and post spirometry continues to be normal. After each visit, the following will be provided to the provider and patient: a letter summarizing the interpretation of the findings using GOLD/GINA criteria with recommendations for initial guideline driven therapy based on GOLD/GINA guidelines, if appropriate. Subjects will be managed by their PCP thereafter.

3. All spirometry test results and the subject's assessment at the time of the test will be uploaded into the subject's electronic health record for future reference.

C) Patient subject- Usual Care:

On the day of the outpatient visit, subjects will be advised to arrive 60 minutes prior to their clinic visit in the same building as the clinic site or the CRC (Clinical Research Center). The following will be performed.

1. Subject demographic and contact information
2. Co-morbid conditions
3. Smoking history
4. Medication history from patient and also from pharmacy used by subjects
5. A respiratory exacerbation history in the past year
6. Modified Medical Research Counsel (mMRC) dyspnea scale and COPD assessment test
7. Quality of life measures

Subjects will be advised to go to their clinics and be managed by their PCP thereafter.

At the end of the 1 year followup, the patient will be scheduled for a pre and post BD spirometry and undergo the same spirometry protocol (de-escalation protocol) as the intervention group.

Based on spirometry findings:

1. If the spirometry findings are consistent with COPD and/or asthma, the following will be provided to the provider and patient: a letter summarizing the interpretation of the findings using GOLD/GINA criteria with recommendations for initial guideline driven therapy based on GOLD/GINA guidelines. Subjects will be managed by their PCP thereafter.

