- 2. List of current respiratory medications from subject's pharmacy and verification with patient
- 3. Use of diagnostic testing: ECG, echocardiograms, CT/CXR, stress testing, cardiac catheterization, other pulmonary function tests
- 4. Any ED visits or hospitalizations or acute outpatient care visit and associated cause.
- 5. Healthcare utilization outside of U of I system (e.g. testing such as spirometry, ED and hospitalizations) if available through scanned records

3) All subjects will be contacted every 3 months after the initial visit via telephone (T_1 , T_2 , T_3 , T_4) up to one year; or they will be given the option to complete in person based on subject's convenience, for example they have a doctor appointment near time of study follow-up. These phone calls will be used to obtain follow-up data since last study contact. A reminder post-card will be mailed to the subjects a month before the next telephone contact.

- 1. Change in type of health insurance or self-pay

2. List of current respiratory medications from subject's pharmacy and verification with patient
3. Use of diagnostic testing: ECG, echocardiograms, CT/CXR, stress testing, cardiac catheterization, other pulmonary function tests
4. Any ED visits or hospitalizations or acute outpatient care visit and associated cause.
5. Healthcare utilization outside of U of I system (e.g. testing such as ancillary testing, ED and hospitalizations)
6. mMRC
7. A respiratory exacerbation history
8. EQ-5D 5L +B Bolt-on
9. SF-36 short form (at 3, 6 and 12 months)
10. Social support survey (at 6 months and 12 months)

F) Monetary compensation of subjects

1. PCP compensation:

UI Health and MSHC PCPs will receive \$95 in cash after completion of the education session. For CCHHS PCPs, the Division or Department will receive a total of \$95 per participant to be part of the divisional fund to be used by the PCP at their discretion as allowed by their institution.

2. Patient subject compensation:

Baseline visit (Vo):

Same for Intervention and usual care groups: Subjects will be provided \$75 in cash for completing the initial study visit.

Telephone contact (T₁-T₃):

Same for Intervention and usual care groups. Subjects who choose to complete the follow-up in person or via telephone will receive \$20 in cash at the time of the visit or at a later specified time that is convenient for the subject.

Final contact (T₄):

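### Section 6 omits medication withdrawal from the study risks, and the exacerbation data that would measure its harm most directly have no planned analysis

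*Combined protocol and SAP*

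**What the plan says.** **Risks (section 6).** Two sources of risk are described. On the test: "Risks and discomforts associated with spirometry are possible". On albuterol: "A medication that can open subjects' airways may be used during spirometry testing". Withdrawal of medication is not mentioned. The Data Safety Monitoring Plan says "few, if any, intervention-related adverse events are anticipated in this study" and describes the population as at risk of poor outcomes, among them "life-threatening exacerbations and death not caused by the study itself". The investigator reviews a monthly report that covers intervention activities and adverse events, and any adverse event is reported promptly to the IRB.

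**Procedures (section 4B).** If spirometry is normal and the PCP approves, respiratory medication is reduced stepwise. With further PCP approval, "deescalation and repeat spirometry can occur in 1-2 week intervals until all maintenance medications are discontinued", provided spirometry stays normal. A de-escalation screener and a phone script are named, but their content is not given.

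**Usual care (section 4C).** After the one-year follow-up, these patients "undergo the same spirometry protocol (de-escalation protocol) as the intervention group".

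**Outcomes and data (sections 4D, 4E and 5).** Primary outcome (ii) is acute outpatient visits, ED visits and hospitalizations, both all-cause and respiratory. Quality of life is secondary. "A respiratory exacerbation history" is item 7 of the three-monthly contacts, and past-year exacerbations are recorded at baseline in both arms. Exacerbations are in neither outcome list. Section 5 names misdiagnosis, quality of life, healthcare utilization and costs as the quantities to be analysed.

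**The concern.** Everyone enrolled uses a maintenance respiratory medication, and the program may lead to all of it being stopped in patients with normal spirometry. Section 6 reads as if the intervention were a breathing test and a bronchodilator. It gives no criterion for separating background exacerbations from those that follow study-prompted withdrawal, and nothing flags the latter for attention.

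The analysis plan does not fill the gap directly. An exacerbation managed without an acute visit is recorded at follow-up but then enters no stated comparison. One that leads to acute care is counted within total utilization, where a rise is hard to interpret: section 5 itself expects that the program may increase other care in patients found free of respiratory disease. The trial could therefore finish without a direct estimate of a plausible harm of its own procedure, although the data for one would be in hand.

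**Working it through.** The documents give no event rate, withdrawal rate, ICC, arm size or power figure, so there is no figure to reproduce. The check is mainly a comparison of sections, with two illustrations of size.

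**1. Sections side by side**

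| Item | Section 4 | Sections 5 and 6 |
|---|---|---|
| Withdrawal of maintenance medication | Study procedure (B, C) | Not among the risks (6) |
| Exacerbations leading to acute care | Within primary outcome (ii) (D) | Compared by group and time, two-sided 0.05 (5) |
| Exacerbations without acute care | Collected at baseline and T1-T4 (B, C, E) | No analysis stated (5) |
| Adverse events | No outcome listed (D) | Reviewed monthly and reported (6); no analysis by arm (5) |
| Start of usual-care withdrawal | After the one-year follow-up (C); near the end of the study (F) | No later outcome contact |

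Section 4F also pays usual-care patients once, for completing both the one-year spirometry and the follow-up. The order of the T4 data and the start of withdrawal is therefore not fixed beyond doubt.

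**2. How many patients might enter withdrawal (illustration)**

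Assumptions: about 500 patients (section 3) split equally, giving 250 per arm; the 30-50% misdiagnosis range from the Background as a proxy for the share withdrawn.

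- 0.30 × 250 = 75
- 0.50 × 250 = 125

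**3. How far the whole-arm comparison dilutes harm (illustration)**

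Assumptions: 20-30% of usual-care patients have at least one respiratory acute-care event in the year; 30-50% of the intervention arm is withdrawn; withdrawal adds 10-15 percentage points of risk in those patients; ICC is 0 to 0.05.

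- Whole-arm difference = share withdrawn × added risk: 0.30 × 0.10 = 0.030, up to 0.50 × 0.15 = 0.075.
- Mean cluster size, with the maximum of 80 PCPs: m = 500/80 = 6.25.
- Design effect = 1 + (m − 1) × ICC: 1.00 at ICC 0; 1 + 5.25 × 0.05 = 1.2625 at ICC 0.05.
- Effective n per arm: 250, or 250/1.2625 = 198.0.
- Power = Φ{[d − 1.96·√(2p̄(1−p̄)/n)] / √([p₀(1−p₀)+p₁(1−p₁)]/n)}, where d = p₁ − p₀ and p̄ is the mean of p₀ and p₁.

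Most favourable corner (p₀ = 0.20, p₁ = 0.275, n = 250): (0.075 − 1.96 × 0.03806)/0.03791 = 0.01; power 0.504.

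Least favourable corner (p₀ = 0.30, p₁ = 0.33, n = 198.0): (0.030 − 1.96 × 0.04668)/0.04666 = −1.32; power 0.094.

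The range is about 9% to 50%. A count or repeated-measures model would change these values.

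**The case against.** A reader might infer that harm from withdrawal would go untested. The documents do not support that. Primary outcome (ii) counts acute visits, ED visits and hospitalizations whatever their cause, so a visit not coded as respiratory still counts. The comparison is two-sided and by intention to treat, so it can show harm as well as benefit. Exacerbations without a visit may also register in the quality-of-life measures. This part of the objection stands: the comparison is indirect and diluted, but it exists.

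A reader might also infer that events after withdrawal would be classed as unrelated. The phrase in section 6 can be read as describing background risk; no relatedness rule follows from it, and any adverse event goes to the IRB. That stands too. What remains is that the text gives no way to tell the two kinds of event apart.

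Section 4 contains real safeguards: PCP approval at each stage, repeat spirometry, continuation only while results stay normal, and a screener. Consent pages were removed from the text reviewed. So it cannot be said that withdrawal risk is unrecognised across the study, only that section 6 does not list it. Safeguards limit harm, but they do not measure or report it.

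It is tempting to add that withdrawn patients' visits are less likely to be coded as respiratory. That is conjecture. Finally, a table by withdrawal status would use a post-randomization subgroup with no usual-care counterpart during the year. That is correct, and it limits what such a table can show.

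**Conclusion.** The point holds as a gap in the safety section and in the analysis of data already collected. Section 6 does not match section 4 on what the intervention involves. Exacerbations without acute care, and adverse events by arm, have no stated analysis. More serious harm is compared only through whole-arm utilization and quality of life.

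Its size cannot be fixed from the documents. The 75-125 patients depend on an equal split that is not stated (the 250 in section 3 is per health system) and on a misdiagnosis share that is neither a withdrawal rate nor an upper bound for one. The 9-50% power range rests wholly on the assumed rates, added risk and ICC; it shows that the indirect comparison could easily miss harm, not that it would.

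The usual-care timing is a matter to clarify. The documents do not show that withdrawal contaminates the 12-month comparison. The sponsor should make the change, because it would yield a direct between-arm estimate of harm that the present plan would not produce.

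**What to change.** 1. **Reconcile section 6 with sections 4B and 4C.** Name medication withdrawal among the study risks. Limit the statement about events not caused by the study to background risk. In the existing monthly report, flag events after withdrawal as possibly intervention-related.
2. **Add a safety outcome to section 4D.** Use patient-reported respiratory exacerbations since the last contact (any, or a count) at T1-T4, with the study team stating what is counted. Compare the randomized arms by intention to treat in the section 5 mixed model, and report an estimate with a 95% CI. It is descriptive for safety and spends no alpha.
3. **Label any table by withdrawal status as descriptive only**, for the reason given under the objection.
4. **Reconcile sections 4C and 4F on timing**, so that usual-care 12-month data are clearly collected before withdrawal begins in that arm.

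The cost is protocol wording and one more comparison to report, with no new data collection. Nothing here proposes how or when medication should be changed.

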7. DATA MANAGEMENT

Confidentiality

To help ensure that patients' health information remains private, we will restrict access to data collected for our study to study personnel only (via use of password-protection and locked cabinets for study documents). Study ID numbers will be generated and will be used when discussing and/or reviewing data at study meetings. Also, study reports will report results in aggregate and not contain information that can be used to identify individual patients.

Storage of Data

Data will be collected from participants in the form of questionnaires and will be documented in the secure, password protected, web-based Research Electronic Data Capture (REDCap) database available only to members of the research team. The research data will be stored securely using subject ID numbers and kept for 6 years after the end of the study.

UI Health electronic medical records(EMR) (inpatient and outpatient) will be reviewed by staff from UI Health and CCHHS EMR (inpatient and outpatient) will be reviewed by staff from CCHHS . Data collected from both institutions will be input into REDCap. The crosswalk file with direct identifiers to the coded data will be created, encrypted, and kept on [name] office computer at [name] and stored such that only authorized individuals will have access to patient identifying information. Hardcopies of the data will not be made.

REFERENCES

- 1 National Center for Health Statistics. Chronic Obstructive Pulmonary Disease Among Adults Aged 18 and Over in the United States, 1998-2009, 2011
- 2 Centers for Disease C, Prevention. Vital signs: asthma prevalence, disease characteristics, and self-management education: United States, 2001--2009. *MMWR Morb Mortal Wkly Rep* 2011; 60:547-552.
- 3 In: Balogh EP, Miller BT, Ball JR, eds. *Improving Diagnosis in Health Care*. Washington (DC), 2015
